### 5.5. Electrocardiogram

Triplicate 12-lead ECG will be obtained at Day 1 (predose), otherwise a single, 12-lead ECG will be obtained at each scheduled time point. The ECG variables that will be analyzed are heart rate (HR), ECG intervals (RR, PR, QRS, and QT) as well as corrected QT intervals according to Bazett's formula (QTcB) and Fridericia's formula (QTcF).

Summary tables for actual values and changes from baseline will be presented by treatment group and period at each scheduled time point and at endpoint. Mean-SE plots over time will be presented for ECG values by treatment group. Scatter plots of post-baseline versus baseline values will be presented by treatment group.

The frequency of subjects who have abnormal values will be summarized by treatment group and study period. All data for subjects that have abnormal values will be presented in a separate listing. The following abnormality ranges will be used for ECG parameters (Table 6):

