6. Has a current or recent history of clinically significant suicidal ideation within the past 6 months, corresponding to a score of 4 (active suicidal ideation with some intent to act, without specific plan) or 5 (active suicidal ideation with specific plan and intent) for ideation on the Columbia Suicide Severity Rating Scale (C-SSRS), or a history of suicidal behavior within the past year, as validated by the C-SSRS at screening or Day 1. Subjects with a prior suicide attempt, or prior serious suicidal ideation/plan ≥ 6 months ago, should be carefully screened for current suicidal ideation and only included at the discretion of the investigator.
7. Subject has a history of or current thyroid disease, thyroid dysfunction and is currently untreated for it. Subjects treated for thyroid disease may be enrolled following review of their records of diagnosis and treatment history by the investigator and with written concurrence with the sponsor's medical monitor to ensure disease/treatment stability and compliance.
8. Criterion modified by Amendment 2.
 - 8.1. Subject has clinically significant abnormal findings on physical examination, neurological examination or clinically significant abnormal vital signs indicative of untreated illness (such as infection or hypertension).
9. Criterion modified by Amendment 5.
 - 9.1. Subject has a clinically significant abnormal finding on 12-lead ECG such as QTcF (QTcB if ECG machine only shows QTcB) >450 msec for males and females, Left Bundle Branch Block, AV Block second degree or higher, permanent pacemaker or implantable cardioverter defibrillator (ICD) at screening or baseline (Day 1 predose), or any finding which in the opinion of the investigator is not appropriate and reasonable for the population under study. ECG recordings and vital signs may be repeated once and for questions on findings on the ECG a local cardiologist should be consulted.
10. Criterion modified by Amendment 5.
 - 10.1 Subject has a history of or current liver or renal insufficiency; clinically significant cardiac, vascular, pulmonary, gastrointestinal, endocrine, hematologic, rheumatologic, psychiatric, or metabolic disturbances (e.g. unstable situation needing monitoring or regular dose adaptations). Subjects with renal or liver function analytes significantly higher (more than 1.5 times the upper limit of normal) at screening are not eligible for the study.

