11.3. Safety Analysis^a

All subjects receiving at least one dose of study drug will be included in the safety analysis. All safety analyses will be performed based on the safety analysis set, which will include all randomized subjects who receive at least 1 dose of study drug.

Adverse Events

The verbatim terms used in the CRF by investigators to identify adverse events will be coded using the Medical Dictionary for Regulatory Activities (MedDRA). All reported adverse events with onset during the double-blind treatment phase (i.e., treatment-emergent adverse events, and adverse events that have worsened since baseline) will be included in the analysis. For each adverse event, the percentage of subjects who experience at least one occurrence of the given event will be summarized by treatment group. Summaries will be provided for all subjects receiving at least one dose of study drug in this study, and will include adverse events from this study.

Summaries, listings, datasets, or subject narratives may be provided, as appropriate, for those subjects who die, who withdraw due to an adverse event, or who experience a severe or a serious adverse event.

Clinical Laboratory Tests

Laboratory data will be summarized by type of laboratory test. Descriptive statistics will be calculated for each laboratory analyte at baseline and at each scheduled time point, and for changes from baseline.

The number and percentage of subjects experiencing a laboratory result below or above normal reference ranges will be provided for each laboratory analyte by treatment group. Summaries will be provided for all subjects receiving at least one dose of study drug in this study.

A listing of subjects with any laboratory result outside the reference ranges will be provided.

12-Lead ECG

Heart rate and ECG intervals (RR, PR, QRS and QT) as well as corrected QT intervals according to Bazett's formula (QTcB) and Fridericia's formula (QTcF) from the 12-lead ECG will be summarized at baseline and at each scheduled time point and for changes from baseline using descriptive statistics.

The number and percentage of subjects with at least one occurrence of a treatment-emergent potentially clinically important QTc measurement (QTc value >450, >480, or >500 msec) or with a change from baseline in QTc >30 msec will be summarized by treatment group.

^a This section has been amended per Amendment INT-2.

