### 2.4. Analysis Timepoints and Phases

Please refer to the time and events schedule in the latest version of the protocol for analysis timepoints per assessment.

**Baseline (reference time point):** for each of the Lead-in, DB Treatment and Withdrawal Period, the reference assessment, i.e. baseline, is the measurement the closest, and prior to the first study medication administration of that period. The baseline measurement may be taken from a scheduled or unscheduled visit.

**End Point for double-blind treatment period:** end point is defined as the last non-missing post-baseline observation during the double-blind treatment period. End point will be defined only for the double-blind treatment period.

Analysis phases will be constructed as follows:

Analysis Phase	Start Date/time	End Date/time
Screening	00:00 of the date of signing the informed consent	1 minute before the first study medication administration in the Lead-in Period
Lead-in Treatment Period	Date/time of the first study medication administration in the Lead-in Treatment Period	1 minute before the first study medication administration in the Double-Blind Treatment Period

		If the subject does not enter the Double-blind Treatment Period then use 23:59 of the day before the date of the first Follow-Up visit
Double-Blind Treatment Period	Date/time of the first study medication administration in the Double-Blind Treatment Period  If the subject takes the morning dose on the day of randomization prior to the randomization (i.e. a dose of the lead-in medication), the time of morning intake of the next day is not known. The start date of the double-blind treatment period will be the day after the day of randomization, and the time of intake will be imputed as 0:00.	1 minute before the first study medication administration in the Withdrawal Treatment Period.  If the subject does not enter the Withdrawal Treatment Period then use 23:59 of the day before the start of the Follow-Up period.
Withdrawal Treatment Period	Date/time of the first study medication administration in the Withdrawal Period	Day 77 visit or early withdrawal visit for subjects who dropout early.
Follow-up	00:00 of the date after the Day 77 visit or early withdrawal visit for subjects who dropout early.	23:59 of the day of study termination (date of last contact)

The last phase, whichever it is for a subject, always ends on 23:59 of the day of study termination (last contact).

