**Table 4: Vital Signs Abnormality Ranges (Supine and Standing)**

	Low	Normal	High
SBP (mmHg)	<90	90-140	>140
DBP (mmHg)	<50	50-90	>90
Pulse (bpm)	<45	45-90	>90
Temperature (C)	<35.5	35.5-37.5	>37.5

The incidence of subjects who have a treatment-emergent abnormality (as defined in Table 5 below) at each scheduled time point and endpoint will be presented by treatment group and study period.

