**Table 6: ECG Abnormality Ranges**

	Low	Normal	High
HR (bpm)	$< 45$	45-90	$> 90$
PR Interval (msec)	$< 120$	120-220	$> 220$
QRS Interval (msec)	-	$< 120$	$\geq 120$
QT Interval (msec)	-	$< 500$	$\geq 500$

Criteria for abnormal corrected QTc interval values and changes from baseline are presented in Table 7. Abnormal values and changes will be summarized using frequency distribution tables over time by treatment group and period. A listing of subjects meeting any of the abnormality criteria will be provided.

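### SAP 5.5 tabulates absolute QTc classes where Protocol 11.3 promises per-subject treatment-emergent counts, which dilutes the new-onset comparison, mainly above 450 msec

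*SAP*

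**What the plan says.** Protocol 11.3 (12-Lead ECG) asks for the number and percentage of subjects, by treatment group, with a "treatment-emergent potentially clinically important QTc measurement (QTc value >450, >480, or >500 msec) or with a change from baseline in QTc >30 msec". For the other ECG measures it asks only for descriptive statistics of values and changes: "Heart rate and ECG intervals (RR, PR, QRS and QT) as well as corrected QT intervals".

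SAP 5.5 has two counting rules. The first introduces Table 6 (HR, PR, QRS, QT): "The frequency of subjects who have abnormal values will be summarized by treatment group and study period". The second introduces Table 7 (QTc): "Abnormal values and changes will be summarized using frequency distribution tables over time by treatment group and period". Table 7 sets absolute QTc classes (up to 450, above 450 to 480, above 480 to 500, above 500) and change classes (up to 30, above 30 to 60, above 60). Only the change classes refer to baseline. The term treatment-emergent does not occur in SAP 5.5.

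The SAP does set a baseline condition in neighbouring sections. In 5.3, a laboratory value is treatment-emergent markedly abnormal only if the baseline was missing, normal, or beyond the opposite limit. In 5.4, "The incidence of subjects who have a treatment-emergent abnormality (as defined in Table 5 below") is reported in addition to the plain abnormality ranges.

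SAP 2.4 supplies the baseline that such a rule needs. For each period, the reference value "is the measurement the closest, and prior to the first study medication administration of that period".

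**The concern.** Two things are lost between protocol and SAP. The protocol's count is per subject (at least one occurrence) and limited to treatment-emergent values. The SAP's is a distribution over time of absolute classes. A subject who is above 450 msec at double-blind baseline and stays there appears in the on-treatment class as if the finding were new.

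Such subjects are expected in both arms alike. They add the same background to each rate, pull the ratio between arms towards 1 and add chance variation. Overall safety and tolerability are part of the primary objective (SAP 1.1), and this is the ECG count that the protocol singles out, so it should be produced as specified.

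Entry criteria reduce the problem but do not remove it. Criterion 9.1 in Protocol 4.2 excludes a subject when the "Subject has a clinically significant abnormal finding on 12-lead ECG such as QTcF (QTcB if ECG machine only shows QTcB) >450 msec" at screening or Day 1. QTcB is limited only where the machine shows nothing else, yet SAP 5.5 analyses both corrections. Double-blind baseline also comes after a 3-week lead-in (SAP 1.2), so values can rise above the limit in between.

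**Working it through.** **Text comparison**

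| | Protocol 11.3 | SAP 5.5 |
|---|---|---|
| QTc >450, >480, >500 | per subject, treatment-emergent, by arm | absolute classes over time, by arm and period, no baseline condition |
| QTc change >30 | per subject, by arm | kept, as classes >30–60 and >60 |
| HR, PR, QRS, QT | descriptive statistics only | adds abnormality counts, no baseline condition |

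The conflict is in the first row. The documents state no ECG rate, so there is no figure to reproduce.

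**Size of the dilution (illustration)**

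Inputs:
- Subjects per arm: 140 × 0.90 / 2 = 63, from the 140 entrants and 10% lead-in drop-out in SAP 1.4.
- New-onset rate p: 2% on placebo and 10% on drug (assumed).
- Share q already abnormal at double-blind baseline and remaining so: 0 to 20% (assumed).

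Formulas:
- Rate shown when all abnormal values count = q + (1 − q)p.
- Difference shown = (1 − q) × (0.10 − 0.02).
- Treatment-emergent rate = p, among 63(1 − q) subjects per arm.

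At q = 5%, placebo shows 0.05 + 0.95 × 0.02 = 6.9% and drug shows 0.05 + 0.95 × 0.10 = 14.5%. The difference is 7.6 points and the ratio is 14.5/6.9 = 2.1.

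| q | Shown, placebo vs drug | Difference (points) | Ratio | Power, all values | Power, treatment-emergent |
|---|---|---|---|---|---|
| 0 | 2.0% vs 10.0% | 8.0 | 5.0 | 47% | 47% |
| 5% | 6.9% vs 14.5% | 7.6 | 2.1 | 28% | 45% |
| 10% | 11.8% vs 19.0% | 7.2 | 1.6 | 20% | 43% |
| 20% | 21.6% vs 28.0% | 6.4 | 1.3 | 13% | 39% |

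Power is for a two-sided 5% comparison of two proportions. No ECG test is planned, so it serves only to gauge how visible a difference would be.

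**Where q could be non-trivial**

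Assume QTcB with mean 415 to 425 msec, between-subject SD 17, within-subject SD 10 and no drug effect. The SD of one reading is √(17² + 10²) = 19.7.
- Above 450 at baseline: z = 35/19.7 to 25/19.7, giving 3.8% to 10.2%.
- Above 480: 0.05% to 0.26%. Above 500: under 0.01%.
- Simulating the three double-blind ECG visits (Weeks 2, 4 and 6), 32% to 42% of subjects with any on-treatment value above 450 were already above it at baseline.
- Applying a 450 limit at screening and to the Day 1 triplicate mean (the case for QTcF, or for machines that show only QTcB) lowers baseline prevalence to 1.8% to 4.2%, and that share to 17% to 21%.

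Dilution is therefore a matter of the 450 threshold, and more of QTcB than of QTcF.

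**The case against.** The strongest reply is that this is a narrow wording gap and that other planned output covers most of it. SAP 5.5 gives changes from baseline by arm and period, QTc change classes, scatter plots of post-baseline against baseline values, and listings of abnormal subjects. The QTc tables are by visit, and Table 1 gives the double-blind baseline its own row, so a reader can compare before and after. This stands as far as detecting a shift goes. None of these outputs is the per-subject count of new values above 450, 480 or 500 that the protocol names.

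Three stronger readings are tempting, and the documents do not support them.
- A reader might infer that Protocol 11.3 also requires treatment-emergent counts for HR, PR, QRS and QT. It asks for no abnormality count of these. A baseline condition on Table 6 would be for consistency with the SAP's laboratory and vital-sign rules only.
- A reader might infer that pre-existing findings mask a drug effect. Randomization balances them in expectation, and in the illustration the absolute difference falls only by the factor 1 − q.
- A reader might infer that the SAP counts pre-dose tracings as on-treatment. SAP 2.4 starts the double-blind phase at the first double-blind dose, so by time they belong to lead-in. Table 1 nevertheless labels the DB Treatment Baseline row with the DB Treatment phase. The text is ambiguous, and no more than that.

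It is also fair to say that the rates above are assumptions, and that a treatment-emergent rule is not free of noise. Double-blind baseline is a single tracing. Under the QTcB model without an entry limit, 5% to 11% of subjects would be flagged above 450 with no drug effect at all.

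**Conclusion.** The point holds for QTc. SAP 5.5 and Table 7 do not deliver the treatment-emergent count in Protocol 11.3. Followed as written, they count subjects who were already above a threshold at double-blind baseline. The consequence is dilution of the new-onset comparison, mainly above 450 msec and for QTcB, and little at 480 or 500.

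Its size depends on baseline prevalence, which the documents do not give. It is nil at q = 0. At q = 5% to 20%, with full persistence and the assumed 2% and 10%, the ratio falls from 5.0 to between 2.1 and 1.3, and the difference from 8.0 to between 7.6 and 6.4 points. No stated figure in either document is wrong.

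**What to change.** In SAP 5.5 add, for the double-blind period and separately for QTcF and QTcB, a per-subject table by arm of treatment-emergent QTc >450, >480 and >500 msec:
- **Event:** at least one post-baseline double-blind value above the threshold in a subject whose double-blind baseline was at or below it.
- **Denominator:** subjects at or below that threshold at double-blind baseline who have a post-baseline double-blind value.
- **Thresholds:** cumulative, so that a baseline above 480 also removes a subject from the >450 denominator.
- **Baseline record:** state that the DB Treatment Baseline record in Table 1 is not a post-baseline value.

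Keep the planned by-visit and change-from-baseline tables. Optionally, for consistency with SAP 5.3 and 5.4 although the protocol does not require it, apply the same condition to Table 6. Do so separately for low and high values, because those ranges are two-sided.

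The cost is one rule and one extra table per correction formula from data already collected, with slightly smaller denominators. Single-tracing noise near a threshold will still flag some subjects in both arms.

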**Table 6: ECG Abnormality Ranges**

	Low	Normal	High
HR (bpm)	$< 45$	45-90	$> 90$
PR Interval (msec)	$< 120$	120-220	$> 220$
QRS Interval (msec)	-	$< 120$	$\geq 120$
QT Interval (msec)	-	$< 500$	$\geq 500$

Criteria for abnormal corrected QTc interval values and changes from baseline are presented in Table 7. Abnormal values and changes will be summarized using frequency distribution tables over time by treatment group and period. A listing of subjects meeting any of the abnormality criteria will be provided.

**Table 7: Criteria for Abnormal QTc Values and Changes From Baseline**

Parameter	Classification	Criteria
QTc value	Normal	$\leq 450$
	> 450 – 480	>450 - $\leq 480$
	> 480 – 500	>480 – $\leq 500$
	> 500	> 500
QTc change from baseline	No concern	$\leq 30$
	Concern	>30 – 60
	Clear concern	> 60

*These criteria are based on ICH E14 Guideline*

## 5.6. C-SSRS

The Columbia Suicide Severity Rating scale (C-SSRS) is a low-burden measure of the spectrum of suicidal ideation and behavior. It is a semi structured clinician-administered questionnaire designed to solicit the occurrence, severity, and frequency of suicide-related ideation and behaviors during the assessment period.

Using the C-SSRS, potentially suicide-related events will be categorized using the following scores:

### Suicidal Ideation (1-5)

- 1: Wish to be dead
- 2: Non-specific active suicidal thoughts
- 3: Active suicidal ideation with any methods (not plan) without intent to act
- 4: Active suicidal ideation with some intent to act, without specific plan
- 5: Active suicidal ideation with specific plan and intent

### Suicidal Behavior (6-10)

- 6: Preparatory acts or behavior
- 7: Aborted attempt
- 8: Interrupted attempt
- 9: Non-fatal suicide attempt
- 10: Completed suicide

A frequency distribution at each scheduled time point and endpoint will be provided by treatment group and study period. A listing will be provided of C-SSRS items throughout the study for subjects with suicidal ideation or behavior at any time point.

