- ^j Refer to study exclusion criteria for circumstances in which a repeat test during Screening is permitted.
- ^k Performed for all women. Serum and urine pregnancy test. Investigators may perform additional pregnancy testing at their discretion as clinically needed.
- ^l At each time point, a venous blood sample will be collected for PK analysis of JNJ-42165279 concentration at predose (i.e., prior to morning dose on Days 14, 35, 63 and 77) and 2 to 4 hours postdose.
- ^m Samples must be collected prior to dosing under fasting conditions whenever possible.
- ⁿ Subjects will be asked to provide a small amount of saliva the night before and upon awakening the morning of the scheduled visit.
- ^o A venous blood sample will be collected for the FAAs (AEA, PEA and OEA). The Visit 2 sample must be taken before the first dose of JNJ-42165279 /placebo.
- ^p Concomitant therapies must be recorded throughout the study beginning with signature of the ICF to the final follow up visit (Visit 11).
- ^q Baseline version completed at screening.
- ^r HDRS₁₇ anxiety/somatization factor score determined from the assessment.
- ^s A neurological examination will also be completed in case of adverse event of interest.
- ^t Urine pregnancy test In WOCBP only. If the urine pregnancy test is positive, a serum β -hcg test will be performed. Investigators may perform additional pregnancy testing at their discretion as clinically needed.

ATRQ = Antidepressant Treatment Response Questionnaire; **CGI-I**=Clinical Global Impression – Improvement; **CPFQ**=Cognitive and Physical Functioning Questionnaire; **C-SSRS** = Columbia Suicide Severity Rating Scale; **CUDOS** = Clinically Useful depression Outcome Scale; **EW** = Early Withdrawal; **HAM-A6** = Hamilton Anxiety Rating scale; **HDRS₁₇** = Hamilton Depression Rating Scale; **MINI** = Mini International Neuropsychiatric Interview; **MOS Sleep-R** = Medical Outcomes Study Sleep-Revised; **PSS** = Perceived Stress Scale; **SHAPS** = Snaith-Hamilton Pleasure Scale; **SIGH-A** = Structured Interview Guide for the Hamilton Anxiety Scale; **SIGH-D**= Structured Interview Guide for the Hamilton Depression Scale

ABBREVIATIONS

Note: Pharmacokinetic Parameters are defined in Section 9.4.3 and questionnaires are defined after the Time and Events Schedule.

AEA	anandamide
ALP	alkaline phosphatase
ALT	alanine aminotransferase
ANCOVA	analysis of covariance
AST	Aspartate transaminase
BMI	Body mass index
CI	Confidence interval

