An example of the PSS is provided in [Attachment 6](#).

Self-Assessment of Treatment Experience

The Self-Assessment of Treatment Experience questionnaire is a 4-item self-report scale designed to provide additional information regarding the subject's subjective experience while taking the treatment. This questionnaire is an internal Janssen scale.

An example of the Self-Assessment of Treatment Experience is provided in [Attachment 8](#).

Safety Evaluations

Clinical Scales

Columbia Suicide Severity Rating Scale (C-SSRS)

An interview to assess the risk of suicidal ideation and behavior will be conducted at each study visit from Screening through the end of the double-blind treatment phase.

The C-SSRS is a low-burden measure of the spectrum of suicidal ideation and behavior that was developed in the National Institute of Mental Health Treatment of Adolescent Suicide Attempters Study to assess severity and track suicidal events through any treatment (Posner 2007). The C-SSRS is a clinical interview providing a summary of both ideation and

behavior that can be administered during any evaluation or risk assessment to identify the occurrence and intensity of suicidal thoughts and suicidal behaviors. It can also be used during treatment to monitor for clinical worsening.

If a suicide-related thought to behavior is identified at any time during the study, a thorough evaluation will be performed by a study physician, and appropriate medical care will be provided.

See [Attachment 9](#) and [Attachment 10](#) for examples of the C-SSRS (baseline) and C-SSRS (since last visit), respectively.

Pharmacokinetic Evaluations

During the study, the sparse blood samples will be collected at the time points indicated in the Time and Events Schedule for PK evaluation in patient population. Concentration time data will allow estimation of individual PK parameters for JNJ-42165279 using a population PK modeling approach. It will also help to understand potential PK differences between healthy subjects and subjects with MDD. Time and days of JNJ-42165279 plasma concentration assessment were chosen to gather maximal information about the PK properties of JNJ-42165279 while minimizing subject burden regarding blood sampling.

Pharmacodynamic Biomarkers

During the study, the following PD evaluations will be performed at the time points indicated in the Time and Events schedule: plasma concentrations of FAAAs (AEA, PEA and OEA).

DNA and Biomarker Collection

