Attachment 9: Columbia Suicide Severity Rating Scale – BASELINE

SUICIDAL IDEATION		Lifetime: Time He/She Felt Most Suicidal
Ask questions 1 and 2. If both are negative, proceed to "Suicidal Behavior" section. If the answer to question 2 is "yes," ask questions 3, 4 and 5. If the answer to question 1 and/or 2 is "yes", complete "Intensity of Ideation" section below.		
1. Wish to be Dead Subject endorses thoughts about a wish to be dead or not alive anymore, or wish to fall asleep and not wake up. Have you wished you were dead or wished you could go to sleep and not wake up? If yes, describe:	Yes No  	
2. Non-Specific Active Suicidal Thoughts General, non-specific thoughts of wanting to end one's life/commit suicide (e.g. "I've thought about killing myself") without thoughts of ways to kill oneself/associated methods, intent, or plan. Have you actually had any thoughts of killing yourself? If yes, describe:	Yes No  	
3. Active Suicidal Ideation with Any Methods (Not Plan) without Intent to Act Subject endorses thoughts of suicide and has thought of at least one method during the assessment period. This is different than a specific plan with time, place or method details worked out (e.g. thought of method to kill self but not a specific plan). Includes person who would say, "I thought about taking an overdose but I never made a specific plan as to when, where or how I would actually do it...and I would never go through with it". Have you been thinking about how you might do this? If yes, describe:	Yes No  	
4. Active Suicidal Ideation with Some Intent to Act, without Specific Plan Active suicidal thoughts of killing oneself and subject reports having some intent to act on such thoughts , as opposed to "I have the thoughts but I definitely will not do anything about them". Have you had these thoughts and had some intention of acting on them? If yes, describe:	Yes No  	

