Attachment 10: Columbia Suicide Severity Rating Scale – Since Last Visit

SUICIDAL IDEATION		Since Last Visit
Ask questions 1 and 2. If both are negative, proceed to "Suicidal Behavior" section. If the answer to question 2 is "yes," ask questions 3, 4 and 5. If the answer to question 1 and/or 2 is "yes", complete "Intensity of Ideation" section below.		
1. Wish to be Dead Subject endorses thoughts about a wish to be dead or not alive anymore, or wish to fall asleep and not wake up. Have you wished you were dead or wished you could go to sleep and not wake up? If yes, describe:	Yes No  	
2. Non-Specific Active Suicidal Thoughts General, non-specific thoughts of wanting to end one's life/commit suicide (e.g. "I've thought about killing myself") without thoughts of ways to kill oneself/associated methods, intent, or plan during the assessment period. Have you actually had any thoughts of killing yourself? If yes, describe:	Yes No  	
3. Active Suicidal Ideation with Any Methods (Not Plan) without Intent to Act Subject endorses thoughts of suicide and has thought of at least one method during the assessment period. This is different than a specific plan with time, place or method details worked out (e.g. thought of method to kill self but not a specific plan). Includes person who would say, "I thought about taking an overdose but I never made a specific plan as to when, where or how I would actually do it....and I would never go through with it". Have you been thinking about how you might do this? If yes, describe:	Yes No  	
4. Active Suicidal Ideation with Some Intent to Act, without Specific Plan Active suicidal thoughts of killing oneself and subject reports having some intent to act on such thoughts , as opposed to "I have the thoughts but I definitely will not do anything about them". Have you had these thoughts and had some intention of acting on them? If yes, describe:	Yes No  	

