## 1.2. Trial Design

This is a multi-center, double-blind, placebo-controlled, randomized, parallel-group study in subjects with MDD with anxious distress who have had inadequate response to SSRI/SNRI treatment.

Subjects who meet the inclusion and exclusion criteria and are enrolled will be maintained on the SSRI/SNRI treatment throughout the study to determine whether adjunctive treatment with JNJ-42165279 can reduce symptoms of MDD with anxious distress.

[figure not shown]
For each subject, the study will consist of three phases: a screening phase of up to 4 weeks, a treatment phase lasting up to 11 weeks, and a 3-week post-treatment (follow up) phase. The treatment phase of the trial will consist of 3 periods. The first period is a placebo lead-in of 3 weeks for all subjects, after which subjects will enter the double-blind treatment period when they will be randomly assigned to JNJ-42165279 or continuation on placebo for 6 weeks. Subjects who successfully complete the double-blind treatment period will be treated with placebo during a 2-week withdrawal period. The total study duration for each subject will be approximately 18 weeks.

The end of study is defined as the date of the last visit of the last subject undergoing the trial. Investigators and subjects will remain blinded to the exact duration of the subject lead-in and withdrawal period during the entire study duration.

Approximately 143 subjects will enter the double-blind placebo lead-in period. At the end of the lead-in period, response status of the subjects will be assessed according to the double-blind response criteria based on reduction in HDRS17 relative to lead-in baseline. Both lead-in placebo responders and lead-in placebo non-responders will be randomly assigned in a 1:1 ratio to either 25 mg of JNJ-42165279 or placebo in the treatment period. The primary efficacy analyses will be based on the treatment period data from the lead-in non-responders (94 subjects).

An overall flow diagram of the study is shown in the figure below.

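### SAP 5.6 tabulates C-SSRS results by visit without allowing for a look-back that runs from lifetime to about 7 days to 14 days, and plans no by-arm C-SSRS summary over a whole period

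*SAP*

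**What the plan says.** Protocol section 3.2 says that the suicidality interview "will be conducted at each study visit from Screening through the end of the double-blind treatment phase". The Time and Events Schedule places the C-SSRS at screening and on Days 1, 7, 14, 21, 28, 35, 49, 63 and 77.

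Two forms are attached. Footnote q of the schedule reads "Baseline version completed at screening", and that form (Protocol Attachment 9) heads its ideation column "Lifetime: Time He/She Felt Most Suicidal". The other form (Attachment 10) is headed "Since Last Visit". No text assigns a form visit by visit. Footnote q attaches only to screening, so the natural reading is that Attachment 10 is used from Day 1 onward.

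SAP Table 1 puts all these visits, screening included, in one list of C-SSRS time points. SAP 5.6 then plans this summary: "A frequency distribution at each scheduled time point and endpoint will be provided by treatment group and study period". It also plans a listing for subjects with any ideation or behaviour. Protocol 11.3 promises tabulation by treatment group and nothing more specific. Neither document labels the look-back, or plans a worst-post-baseline category, a shift table or an any-occurrence summary for a period.

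**The concern.** On a since-last-visit form, the length of recall is the gap between visits. When the gap changes, the percentage positive can change while the risk does not. Here the gap lengthens during the double-blind period, after double-blind Week 2. A reader following one arm across the columns cannot tell a change in risk from a change in recall.

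The same applies to endpoint read against double-blind baseline. Under SAP 2.4 that baseline is the Visit 5 assessment, a 7-day report. A completer's endpoint is Week 6, a 14-day report. A dropout's endpoint covers whatever time had passed since the visit before.

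Reports can also drop out of the table. SAP 2.5 keeps one visit per window (the closest to target) and leaves the others out of summaries. An event reported at a visit that is not selected should not be reported again on the next since-last-visit form, so it would survive only in the listing. Protocol 9.1.1 allows extra assessments after abnormal safety findings, so this can happen.

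Safety and tolerability are part of the primary objective and the population is depressed, so the C-SSRS summary should be readable on its own.

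**Working it through.** **Plan's own figure.** The documents give no C-SSRS rate, power or sample size, so there is none to reproduce. The schedule can be checked. SAP 1.2 says "The first period is a placebo lead-in of 3 weeks for all subjects", so protocol days less 21 should give the SAP's double-blind target days: 28 − 21 = 7, 35 − 21 = 14, 49 − 21 = 28, 63 − 21 = 42. For the withdrawal period, 77 − 63 = 14. All match SAP Table 1.

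**Look-back at each visit.** From Day 1 on, this is the gap from the previous assessment. The Day 1 range follows from "a screening phase of up to 4 weeks" (SAP 1.2).

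| Visit | Day | SAP label | Nominal look-back |
|---|---|---|---|
| 1 | −28 to −1 | Screening | lifetime |
| 2 | 1 | Lead-in baseline | 1 to 28 days |
| 3 | 7 | Lead-in Week 1 | 6 days |
| 4 | 14 | Lead-in Week 2 | 7 days |
| 5 | 21 | Lead-in Week 3, double-blind baseline | 7 days |
| 6 | 28 | Double-blind Week 1 | 7 days |
| 7 | 35 | Double-blind Week 2 | 7 days |
| 8 | 49 | Double-blind Week 4 | 14 days |
| 9 | 63 | Double-blind Week 6 | 14 days |
| 10 | 77 | Withdrawal Week 2 | 14 days |

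With the ±3-day visit window, a nominal 7-day gap can be 1 to 13 days and a nominal 14-day gap 8 to 20 days.

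**Effect on the percentage positive at constant risk.** Let p be the proportion positive in any 7 days and ρ the within-subject correlation between adjacent weeks. Both are assumptions. Suppose a 14-day report is positive if either week was. Then

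P14 = 1 − [(1 − p)² + ρp(1 − p)], and P14 / p = 2 − p − ρ(1 − p).

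Example: for p = 5% and ρ = 0.5 the ratio is 2 − 0.05 − 0.5 × 0.95 = 1.475.

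| p | ρ = 0 | ρ = 0.5 | ρ = 0.9 | ρ = 1 |
|---|---|---|---|---|
| 1% | 1.99 | 1.495 | 1.099 | 1.00 |
| 5% | 1.95 | 1.475 | 1.095 | 1.00 |
| 10% | 1.90 | 1.45 | 1.09 | 1.00 |
| 20% | 1.80 | 1.40 | 1.08 | 1.00 |
| 40% | 1.60 | 1.30 | 1.06 | 1.00 |

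**Day 1.** At the maximum 28-day gap, p = 5% and independent weeks give 1 − 0.95⁴ = 18.5%. This too is an upper bound: a shorter screening gap or persistent ideation lowers it.

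**Comparison between arms at the same visit.** Both arms share one schedule. With 10% in each arm, the ratio is 1.00 at either look-back. With 5% against 10% over 7 days the ratio is 2.00. Over 14 independent days it is 0.19 / 0.0975 = 1.95. Equal risks stay equal.

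**The case against.** The case on the other side is substantial, and most of it stands.

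- **Size.** A reader might infer that the table must show suicidality roughly doubling on treatment. The documents do not support that. The look-back doubles; the percentage need not. A ratio near 2 needs rare events unrelated from week to week, which is a poor description of ideation in a continuing depressive episode.
- **Treatment contrast.** A reader might infer that the comparison of arms is biased. At any one visit it is not, and the placebo arm would show the same look-back effect. Only the endpoint column could differ between arms, and then only if the amount or timing of dropout differed. The documents give nothing from which to size that. Nor is a dropout's endpoint always a 7-day report: a last visit at Week 4 covers 14 days, and an early-withdrawal visit covers a variable time.
- **Other summaries.** A reader might take SAP 5.6 for the only by-arm view of suicidality. Protocol Attachment 11 lists suicidal ideation and behaviour among the anticipated adverse events to be captured, and SAP 5.2 tabulates treatment-emergent events by arm and period.
- **Lifetime record.** Screening is its own analysis phase, and the SAP 2.4 rule makes the lifetime report the baseline of no treatment period. The fall from it occurs before any study medication.
- **No planned test.** SAP 5.6 specifies no change from baseline, shift or test for the C-SSRS, and no stopping criterion in Protocol 3.3 uses this table. The listing keeps the raw reports.

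What the objection does not answer is that a table laid out by visit and endpoint invites reading across columns, and that its columns cover unequal time. Adverse-event reporting does not replace a structured interview given to every subject at every visit. A listing is not a by-arm summary.

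**Conclusion.** The point holds as a cheap improvement to a descriptive safety summary. Within an arm, trends across visits and endpoint against double-blind baseline are not like for like. At constant risk, the step from double-blind Week 2 to Week 4 can inflate the percentage positive by a factor from 1.0 to just under 2.0. The lower end applies to fully persistent ideation, the upper to rare, isolated events. Where the trial would fall depends on p and ρ, which the documents do not give. The result also assumes complete recall and use of the since-last-visit form at every visit after screening, which is inferred from footnote q and the attachments.

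The remaining gap is that no by-arm C-SSRS summary over a whole period is planned, and that the one-visit-per-window rule can remove a positive report from the only C-SSRS table there is.

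**What to change.** In SAP 5.6:

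1. Add a by-arm table of the number and proportion of subjects with any ideation (scores 1 to 5) and any behaviour (scores 6 to 10) over the whole lead-in (Visits 3 to 5) and over the whole double-blind period (Visits 6 to 9), with subject-weeks observed in each. Use all scheduled, unscheduled and early-withdrawal assessments, and state that the SAP 2.5 visit-selection rule does not apply to this table.
2. Present the lifetime screening result in its own table or column, apart from the by-visit series.
3. Keep the by-visit table and print the nominal look-back in each column heading. Note that it varies in the endpoint column.

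The cost is a few lines of SAP text and one more table from data already collected. No visit, form or sample size changes.
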